ICD	Implantable cardioverter defibrillator
ICF	Informed consent form
ICH	International Council for Harmonisation
IEC	Independent ethics committee
INR	International normalised ratio
IRAF	Immediate relapse of atrial fibrillation
IWRs	Interactive web randomization system
Kel	Elimination rate constant
LV	Left ventricle
LVEF	Left ventricular ejection fraction
MedDRA	Medical Dictionary for Regulatory Activities
MTD	Maximum tolerated dose
NCA	Non-compartmental analysis
NOAEL	No observed adverse effect level
PCI	Percutaneous coronary intervention
PD	Pharmacodynamics
PK	Pharmacokinetic
QTc	Corrected QT interval
SAE	Serious adverse reaction
SAP	Statistical analysis plan
SD	Standard deviation
SOC	System organ class
SOP	Standard operating procedure
SR	Sinus rhythm
$t_{1/2}$	Terminal half-life
TEAE	Treatment-emergent adverse event
T_{max}	Time at which C_{max} occurs
TSH	Thyroid stimulating hormone
TTE	Transthoracic echo
WHO	World health organisation

This document is confidential.

2. Purpose

The purpose of this statistical analysis plan (SAP) is to ensure that the data listings, summary tables and figures which will be produced, and the statistical methodologies that will be used, are complete and appropriate to allow valid conclusions regarding the study objectives.

2.1. Responsibilities

Syneos Health will perform the statistical analyses and are responsible for the production and quality control of all tables, figures and listings. Pharmacokinetic analysis will also be carried out by Syneos Health.

2.2. Timings of Analyses

The study will be conducted in two parts (Parts 1 and 2): Part 1 of the study is a fixed randomisation placebo-controlled parallel design, and Part 2 will be an adaptive design conducted in one or more further doses of AP30663 vs Placebo.

In Part 1 of the study, up to 36 patients will be randomised in a 1:1 ratio to receive AP30663 at 3 mg/kg or matching placebo. An interim analysis (IA) will be conducted once the randomised patients in Part 1 have completed Day 2 assessments or terminated the study (see section 8.1 of the protocol).

An interim analysis (Part 1) including efficacy, PK/PD, safety and tolerability data will be conducted after all randomised patients have completed Day 2 assessments of the study, in order to determine the starting dose(s) for Part 2 of the study. For further information see section 11. An independent data monitoring committee (DMC) will be convened to review the accumulating unblinded efficacy (including ECG and Holter ECG), PK/PD, safety and tolerability data for the study at the time of the interim analysis.

During Part 2, IAs will occur when 18, 36 and 54 patients have been randomised to open-doses including placebo, and have completed Day 2 assessments or terminated the study.

For Part 2, the DMC will give their recommendations regarding continuation or early termination of the study. Decision rules will be based on the AF conversion rate; however the DMC will also have the option to stop a dose arm (or the study) due to unacceptable safety and tolerability (including but not limited to increase in QTcF interval and number and severity of local injection site reactions).

An unblinded team (unblinded statistician and unblinded programming team) will be responsible for generating and delivering unblinded TFLs to the DMC members. Tables that will be delivered for the interim analysis are detailed in Section 16.

This document is confidential.

3. Study Objectives

3.1. Primary Objective

The primary objective of the study is to demonstrate the efficacy of one or more dose levels of AP30663 on the basis of the ability to convert atrial fibrillation (AF) after intravenous administration.

3.2. Secondary Objectives

The secondary objectives of the study are as follows:

- To study the stability of rhythm control (immediate relapse of AF [IRAF], *i.e.* within 5 min after conversion from AF).
- To study the importance of AF duration with respect to the efficacy and safety of one or more dose levels of AP30663.
- To evaluate the safety and tolerability of one or more dose levels of AP30663.
- To study the relationship between systemic exposure and response, with special regard to the conversion from AF and the effect on QRS and QTcF.

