7.1.2 Secondary Objectives

The secondary objectives of the study are as follows:

- To study the stability of rhythm control (immediate relapse of AF [IRAF], i.e. within 5 min after conversion from AF).
- To study the importance of AF duration with respect to the efficacy and safety of 1 or more dose levels of AP30663.
- To evaluate the safety and tolerability of 1 or more dose levels of AP30663.
- To study the relationship between systemic exposure and response, with special regard to the conversion from AF and the effect on QRS and QTcF.

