- K_{el} : Elimination rate constant. This parameter will be the negative of the estimated slope of the linear regression of the ln-transformed concentration versus time profile in the terminal elimination phase. At least 3 concentration points will be used in estimating K_{el} . The time point where ln-linear K_{el} calculation begins (K_{el} Lower), and the actual sampling time of the last quantifiable concentration used to estimate the K_{el} (K_{el} Upper) will be reported with the correlation coefficient from the linear regression to calculate K_{el}

From the developed population PK model, PK parameters like volume of distribution and clearance will be estimated. Additional PK parameters including but not limited to area under the curve at steady-state will be derived from the individual Bayes estimates from the population PK model.

Software

Population PK analyses will be performed using NONMEM® version 7.4. Analysis datasets and graphical analyses other than non-linear mixed-effect modelling will be performed using R v3.5.0.

Population PK Approach

The population PK model will be developed using the analysis dataset and guided by the results of exploratory analysis. During the model development process, the structural, statistical, and covariate model will be selected. The model developed will be internally qualified using several diagnostics and statistical techniques as non-parametric bootstrap. A complete description of the population PK approach will be presented in a separate PK modelling analysis plan.

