10.6. ECG

A 12-lead digital ECG will be performed at the times outlined in the Study Procedures and Flowchart in Section 3.9 in a standardized manner (*i.e.* after the patient has rested in the [semi]supine position for at least 5 min).

The investigator will assess ECG abnormalities (e.g. ischemia, conduction abnormalities, and rhythm abnormalities) and define the ECG intervals as part of the screening of eligibility and according to the inclusion/exclusion criteria, and as part of an adverse event assessment.

12-lead digital ECG will be overread by the central ECG laboratory. The following measurements will be provided for all PK time points: RR, PR, QRS, QT, QTcF (Fridericia's correction of QT interval), heart rate, as well as T- and U-wave morphology classifications.

Bedside safety ECGs will be collected by the site, printed and reviewed by the investigator on site.

ECG intervals based on these safety ECGs will only be recorded if part of an adverse event.

A summary table for actual and change from baseline will be provided by treatment.

Results for 12-Lead ECGs will be summarized by the number and percentage within each category ("normal", "abnormal, not clinically significant", and "abnormal, clinically significant") .

Abnormal results for 12-Lead ECGs will be summarized as below:

- Absolute QTc interval prolongation:
 - QTc F interval > 450 ms
 - QTc F interval > 500 ms
- Change from baseline in QTc interval:
 - QTc F interval increases from baseline >30 ms
 - QTcF interval increases from baseline >60 ms

ECG data will be listed for all patients, and any clinically significant findings in ECG values will be flagged.

A cardiac Statistical Analysis Plan will be developed by Clario.

This document is confidential.

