APPENDIX I SAMPLE SAS CODE IN STATISTICAL ANALYSIS

1) Sample Code for Efficacy Analysis

The logistic regression will be used to analyze all efficacy endpoints relating to proportions

The following is an example of the SAS codes used to perform the analysis of this LOGISTIC model.

* SAS Codes: *LOGISTIC* model

* Variables in the model:

* resp = proportion of patients who have converted from AF within 90 mn from the start of infusion

* Duration of current AF episode = Dur

*trtp = treatment planned

*****;

```
proc logistic data=eff descending;
class trtp (param=ref ref='Placebo');
model resp (event="Yes")= trtp dur;
```

```
contrast 'Pairwise' trt 1 -1 0 /estimate=exp;
contrast 'Pairwise' trt 1 0 -1 /estimate=exp;
```

```
ods output Contrastestimate=est;
run;
```

A Kaplan-Meier analysis was used for time to conversion. An example of the SAS code to perform this analysis is below.

* SAS Code: Kaplan-Meier Analysis

* Variables in the model:

* timeconv = The time to conversion from AF from start of infusion

* Censor = censor variable (0=patients with conversion, 1=censored patients, no pharmacological conversion)

*trtp = treatment planned

*****;

```
proc lifetest data=dataset plot;
```

This document is confidential.

```
time timeconv*censor(1);
strata trtp/ test=(logrank) diff=control('Placebo');
ods output quartiles/quartile
run;
```

2) Sample Code for graph

```
*****
```

* SAS Code: Graph Concentration response relationship:

QTcF versus AP30663 plasma concentrations

* PCTRESN = Plasma concentration

* AVAL = QTcF

```
*****
```

```
proc sgplot data=PKPD;
reg x=PCSTRESN y=AVAL /CLM alpha=.05;
refline 0/axis=y;
label PCSTRESN="Plasma concentration (unit)";
run;
```

This document is confidential.

AP30663_2001_SAP_Text_4.0_20Feb2023

Final Audit Report

2023-02-20

Created: 2023-02-20

By: PPD [REDACTED]

Status: Signed

Transaction ID: PPD [REDACTED]

"AP30663_2001_SAP_Text_4.0_20Feb2023" History

-  Document created by PPD [REDACTED]
2023-02-20 - 2:01:32 PM GMT- IP address: PPD [REDACTED]
-  Signer PPD [REDACTED] entered name at signing as PPD [REDACTED]
2023-02-20 - 2:04:32 PM GMT- IP address: PPD [REDACTED]
-  PPD [REDACTED] verified identity with Adobe Acrobat Sign authentication
2023-02-20 - 2:04:34 PM GMT
-  Document e-signed by PPD [REDACTED]
Signing reason: I am the author
Signature Date: 2023-02-20 - 2:04:34 PM GMT - Time Source: server- IP address: PPD [REDACTED]
-  Document emailed to PPD [REDACTED] for signature

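### The sample QTcF–concentration graph draws its 95% band from pooled least squares with no patient term, and its zero line does not match the plotted variable

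*SAP*

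**What the plan says.** Protocol 7.1.2 sets a secondary objective, "To study the relationship between systemic exposure and response". SAP 3.2 repeats it, "with special regard to the conversion from AF and the effect on QRS and QTcF".

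For conversion, SAP Section 17 indexes scatter plots of Cmax, AUC and concentration at conversion against time to conversion. For the ECG, the only concentration-based item is the second code block in SAP Appendix I, described as "QTcF versus AP30663 plasma concentrations". Its working statements are "reg x=PCSTRESN y=AVAL /CLM alpha=.05" and "refline 0/axis=y". The comment above the code defines the y variable, AVAL, as QTcF. The input dataset, PKPD, is not defined anywhere in the SAP, and Section 17 does not list this graph.

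SAP 10.6 handles ECG intervals by dose group: "A summary table for actual and change from baseline will be provided by treatment". It closes with "A cardiac Statistical Analysis Plan will be developed by Clario", without giving that plan's scope. Protocol 11.1.5 announces one more document: "A complete description of the population PK approach will be presented in a separate PK modelling analysis plan".

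**The concern.** The REG statement with CLM fits one straight line to every record in the dataset and computes limits for the mean as if all records were independent. Readings from one patient are not independent. Patients differ in QTcF level and probably in sensitivity to the drug, and change-from-baseline values within a patient share one baseline reading. Treating about 10 readings per patient as about 10 patients makes the band too narrow.

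The second fault is internal. A horizontal line at 0 means no effect on a change-from-baseline scale, but is meaningless on an absolute QTcF scale near 400 ms. A programmer following the comment and one following the reference line would produce different graphs.

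At stake is how precisely the mean QTcF, or its rise, at a given concentration appears to be known. The Protocol introduction reports a dose- and concentration-related QTcF effect in Phase 1, with an estimated peak mean of 45.2 ms at 6 mg/kg, the highest dose allowed here.

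**Working it through.** **Pairs per patient.** Protocol 10.1.2.1 states 11 PK sampling times, or 12 with conversion. Counting the schedule reproduces this: pre-infusion, 5, 15, 25, 30 and 45 min, 1 h, 1 h 30 min, 4 h, 8 h and 24 h = 11. Protocol 10.1.1.1 extracts ECGs at the same times except 24 h, and averages triplicates to one value per time. So 11 − 1 = 10 scheduled pairs. A converter could give 11, or 12 if the reference in SAP 10.6 to all PK time points is read literally.

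**Records.** Part 1 has 18 active patients (36 randomised 1:1), so 18 × 10 = 180 records. The maximum number of active patients is 18 + (2/3 × 72) = 66, so 66 × 10 = 660 records.

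**Analytic check at the mean concentration.** There the slope contributes nothing to the error, and the variance of the fitted mean is inflated by 1 + (m − 1) × ICC. The documents give no ICC, so a range is assumed. With m = 10:

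| ICC (assumed) | Design effect | True SE / OLS SE | Coverage of nominal 95% band | Effective size of 180 records |
|---|---|---|---|---|
| 0.2 | 1 + 9 × 0.2 = 2.8 | 1.67 | 76% | 180/2.8 ≈ 64 |
| 0.5 | 1 + 9 × 0.5 = 5.5 | 2.35 | 60% | 180/5.5 ≈ 33 |
| 0.8 | 1 + 9 × 0.8 = 8.2 | 2.86 | 51% | 180/8.2 ≈ 22 |

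Coverage is 2Φ(1.96 / √design effect) − 1.

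**Change from baseline is not a cure by itself.** Suppose each reading has independent error variance σ². Subtracting a shared baseline gives each change score variance 2σ², and any two from one patient share covariance σ², so ICC = 0.5. With nine post-baseline readings the design effect is 1 + 8 × 0.5 = 5, and coverage is 2Φ(1.96/√5) − 1 = 62%.

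**Simulation away from the mean concentration.** All variance and profile inputs are assumptions:
- peak effect 22.6 ms at 3 mg/kg (half of 45.2 ms);
- relative concentrations 0, 0.6, 0.85, 0.95, 1, 0.5, 0.35, 0.25, 0.10 and 0.03;
- concentration CV 25%, and between-patient slope CV 0 or 30%;
- between-patient QTcF SD 5–25 ms and within-patient SD 8–10 ms, giving ICC about 0.2–0.9.

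Results for the nominal 95% least-squares band:
- Half-peak concentration: coverage about 46–77%.
- Peak concentration: about 62–87%. For change from baseline alone, about 64–76%.
- Slope interval: about 83–97%, with the slope itself unbiased.
- 66 active patients instead of 18: no cure, because the true and the computed standard errors shrink together.
- Patient-level jackknife standard errors at 18 patients (ICC 0.5 and above): coverage 93–96%.

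A separate simulation with a slightly different profile and zero within-patient correlation gave 94–95% throughout. Clustering is therefore the cause.

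**The case against.** The strongest reply is that this is not a committed analysis. Appendix I is headed as sample code and has other template slips: the logistic block declares trtp but contrasts trt, and its contrasts suit three levels. The graph is not in the figure index for the final analysis or the DMC. PKPD is undefined, so the pooling of all time points is inferred. All of this stands and limits the weight of the point. It does not make the code right: no averaging or patient term appears, and it is the only specification of this graph in the SAP.

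A second reply is that nothing depends on the band. The dose rules use conversion only, infusion stopping limits use individual QTcF, and the DMC receives change-from-baseline and categorical QTc tables. This is correct. A reader might infer that the narrow band could distort dose selection; the documents do not support that, since no stated decision uses it. The absolute error may also be small. With 66 patients across three doses, one calculation put the band at about ±1.2 to 2.0 ms and too narrow by roughly 1–3 ms, against an assumed rise above 20 ms.

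A third reply concerns QRS. A reader might infer that the QRS part of the objective has been left without an analysis. The documents do not show that. SAP 10.6 announces a cardiac SAP just after describing central reading of QRS and QTcF at the PK times, and that plan may well contain concentration–QRS and concentration–QTcF models. From these documents the gap is at most a missing cross-reference. Phase 1 also reported no effect on other ECG markers.

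**Conclusion.** The point holds for the graph code. As written, the 95% band treats repeated readings from a patient as independent, and the definition of AVAL conflicts with the zero line. If all time-matched records are pooled, coverage is roughly 46–77% at half-peak and 62–87% at peak concentration. These figures rest on assumed variances, concentration profile and CVs. It would be tempting to say the band shows half the true uncertainty; that ratio depends on the assumed SDs and is not a property of the plan. The direction of the error does not depend on them, provided readings within a patient are positively correlated. The slope and its interval are much less affected.

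This is a minor correction to a descriptive graph. It does not touch the primary analysis or the adaptive rules, and it does not show that a QRS analysis is missing.

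**What to change.** First settle whether the cardiac SAP covers concentration–QTcF.

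- **If it does:** delete the graph code from Appendix I and add one sentence in SAP 10.6 that cross-refers to it. The same sentence can say where concentration–QRS is handled.
- **If it does not:** in Appendix I, define AVAL as change from baseline in QTcF so that the zero line applies. State which records enter PKPD. Draw the 95% band from a model with patient random effects, or use patient-clustered standard errors; either is adequate for a descriptive graph. Add the figure to the index in Section 17.

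The cost is one sentence or a few lines of code. No new data are needed, because the central ECG readings and plasma samples share the same scheduled times up to 8 h.

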3.3. Exploratory Objectives

The exploratory objectives of the study are as follows:

- To study demographic and echocardiographic variables, concomitant diseases, and concurrent medication with respect to the efficacy and safety of one or more dose levels of AP30663.
- To evaluate the PK of AP30663, including influence of dose, concomitant medication, concurrent diseases, and demographic variables.
- To explore the proportions of patients on AP30663 converting from AF and of patients randomised to placebo and converting at DC cardioversion.

[figure not shown]
3.4. Brief Description

This is a double-blind, randomised, placebo-controlled, parallel-group Phase 2a study of one or more dose levels of AP30663 for cardioversion in adult patients with AF.

The study will be conducted in two parts (Part 1 and 2): Part 1 of the study is a fixed randomisation placebo-controlled parallel design and Part 2 will be an adaptive design conducted in one or more further doses of AP30663 vs Placebo. The study is designed to identify the dose of AP30663 to be evaluated further in later-Phase research. Though the study investigates multiple doses of AP30663 versus placebo, the participating patients will be randomised to receive one dose of AP30663 (*i.e.* patients will not receive multiple dose levels).

This document is confidential.

Figure 1 Study Schema

Abbreviations: N=number of patients enrolled, P_3 =conversion ratio at 3 mg/kg, P_4 =conversion ratio at d mg/kg, Pr=probability.

*All active AP30663 arms will be randomised equally for each interim analysis; randomisation will occur cumulatively in 2:1 ratio to receive either AP30663 or placebo across all open AP30663 arms.

[†]If one level below this dose (d-1) has never been opened, then dose d-1 will be opened

[‡]If dose 'd' is the highest dose opened so far, and dose 'd' is <6 mg/kg, then dose 'd+1' will be opened.

3.5. Patient Selection

3.5.1. Inclusion Criteria

See section 8.3.2 of the protocol

3.5.2. Exclusion Criteria

See section 8.3.3 of the protocol

3.6. Determination of Sample Size

The study is a proof of concept, designed to allow for a considered testing of a range of doses of AP30663, compared with placebo. Based on the study design, the sample size for randomisation will range from up to 36 to up to 108. The total sample size is dependent on the AP30663 dose arms opened

This document is confidential.

on the decision of the DMC. A total of 4 IAs and a final analysis are included in the design, and so it is foreseen that the total number of randomised patients will be either up to 36, 54, 72, 90 or 108 patients to have a sufficient number of patients evaluable for AF conversion at each IA.

The adaptive design utilises the probability that the response rate at a Dose d is greater than a success rate of 65% ($P_d > 0.65$, where d is the dose arm of AP30663), based on a Bayesian modelling procedure.

3.7. Treatment Assignment & Blinding

For Part 1 of the study, eligible patients will be randomised 1:1 (approximately 36 patients randomised to AP30663 or placebo). An additional 18 to 72 patients will be randomised cumulatively in a 2:1 ratio to 1 or more doses of AP30663 (dependent on dose arms open at time of randomisation) or placebo in Part 2 using an interactive web randomisation system (IWRS).

Two separate lists will be utilised for the study, one for Part 1 and a separate one for Part 2. Both lists will be provided by a separate unblinded biostatistical team and provided to the IWRS.

Acesion Pharma, investigators, and patients will remain blinded to the study treatment allocation until the end of the study. The randomisation list will be kept secure from the study team, investigators, and patients throughout the conduct of the study and until unblinding is authorised by Acesion Pharma and the blinded lead study statistician. The DMC will be unblinded according to the DMC charter, and a separate unblinded statistical team will be assigned to provide the analyses to the DMC and Interim Analysis. Further details of blinded and unblinded personnel will be included in the DMC charter.

3.8. Administration of Study Medication

Study drugs will either be AP30663 or placebo.

Prior to the interim analysis (Part 1 of the study), patients randomised to the AP30663 arm will receive AP30663 at a dose of 3 mg/kg.

The starting AP30663 dose(s) for Part 2 of the study will be determined during DMC review of the interim analysis at the end of Part 1. In Part 2, patients randomised to AP30663 may receive one of the following AP30663 doses: 2, 4, 5, or 6 mg/kg dependent on the results seen for the decision criteria, and the subsequent dose recommended by the DMC.

Patients randomised to the placebo arm will receive matching placebo infusion.

3.9. Study Procedures and Flowchart

The schedule of the planned study assessments during Part 1 and Part 2 is in section 8.1.2 from the protocol. The planned study assessments during Part 2 are the same as those that are planned for Part 1.

This document is confidential.

4. Endpoints

4.1. Primary Efficacy Endpoint

The proportion of patients that have converted from AF within 90 min from the start of infusion and subsequently have no AF recurrence within 1 min of conversion from AF.

